3.4.4. Method of treatment assignment/Randomization

(1) Subject Numbering

Subjects will be assigned a unique consecutive subject number, 3 digits. Preceding the digits will be the letters EM (Exparel/Marcaine) to identify the study. For example, subject numbers will be EM001, EM002, etc., in consecutive order. Subject numbers, once assigned, will not be reused.

(2) Randomization

A randomization schema will be performed by a secondary statistician at the Centers for Clinical Research for all 200 patients and will be listed on one list that will be provided to MMC pharmacy and will also be stored by the Research Coordinators for reference. The patient ID and randomization assignment will be sent to the pharmacy along with screening weight of the subject. The subject(s) and study statistician(s) will remain blinded to the treatment assignments throughout the course of the study while the surgical team and coordinators will not be blinded. Data will be analyzed by the blinded statistician(s) to ensure minimal bias.

(3) Administration and timing of Study drug

Study drug will be administered by the investigator surgeon or members of surgical team under supervision of the investigator surgeon as described below:

Test group A: At the end of the surgical procedure patients in group A will receive injections of liposomal bupivacaine (Exparel, standard dose based on patient's screening weight) delivered via a 25 gauge needle into the surrounding cutaneous and deep tissue including the periosteum around the thoracoscopic port incision sites after closure.

Active Comparator Group B: At the end of the surgical procedure patients in group B will receive, injections of standard bupivacaine HCl with epinephrine 0.25% delivered via 25 gauge needle into the surrounding cutaneous and deep tissue including the periosteum around the thoracoscopic port incision sites after closure.

- *Rationale for Selection of Doses*

Dose will be calculated by the physician based on the screening weight of each randomized patient as is done in the standard way. This will provide reasonable comparison of standard dose of each drug that would have been given for any individual patient.

(4) Treatment compliance

Treatment compliance will be measured in terms of the subject receiving an injection of either Exparel® or Marcaine with epinephrine® from the study personnel. No other forms of compliance will be measured.

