6. DATA MANAGEMENT AND CONFIDENTIALITY

Study coordinators will be responsible for data collection and will ensure that forms are completed and signed. Protected Health Information (PHI) will be recorded for tracking the subjects through the course of the study. Subjects may be assigned IDs for unbiased analysis, however these IDs will be linked to PHI separately. Data will be collected on data collection forms (appendix 1, including AE and medication logs) and subsequently entered into RedCAP for statistical analysis. Original signed consent forms, data collection forms and any relevant source documentation will be maintained for the duration of the study in locked file cabinets inside Cardiothoracic Surgery office suites. Electronic data will be stored on a secure server accessible via password-protected computer. Only authorized study personnel will have access to the study data. After completion of data analysis and final manuscript(s) approval, all non-electronic records will be sent to SIU-Records Management for extended storage. Records will be stored for such a period after study completion as dictated by SIU regulations.

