7. ASSESSEMENT OF SAFETY

Stopping rules and attributes of seriousness, unexpectedness, severity and causality will be assigned by the investigators and further reviewed during monthly meetings, or as needed based on urgency, as part of the data and safety monitoring plan (DSMP).

Summary: Screening eligibility will be reviewed based on standard of care testing done for the elective index procedure. Adverse events (AE) will be monitored and recorded daily throughout the subjects' hospital stay and again at their post-surgical follow-up visits (30 day) and at 6 month and 1 year (part of standard of care) either in person or through review of subjects' EHRs and phone interviews. These will be reviewed individually by the PI and co-investigators and reported by study personnel. An adverse event log will be created for this study. Regularly scheduled meetings of study personnel will take place to review study progress, procedures, AEs and safety considerations. Real time management of AEs will be done per standard of care by the subjects' health care providers. Any serious AE or unanticipated problems will be reported to the Springfield

Committee for Research Involving Human Subjects (SCRIHS) in accordance with SCRIHS policy.

Specification of Safety Parameters: Safety of exparel and marcaine will be evaluated in this study. Safety endpoints will include:

- (1) Adverse events including serious adverse events (SAEs), suspected ADRs, and discontinuations due to AEs
- (2) Physical examination
- (3) Vital signs

Table 1: Schedule of study assessments

Assessment	Baseline/ Screening	Pre-op (D0)	OP (D0)	Each POD	hospital discharge	F/UP (D30 ± 7d)	F/UP (6m)	F/UP (12m)
Inclusion/exclusion	X	X						
ICF	X							
Vitals	X		X	X	X	X	X	X
PE (done as standard of care by any authorized clinical team member)	X		X	X	X	X	X	X
Medical/Surgical History	X							
Concomitant medications (excluding pain Rx)	X	X	X	X	X	X	X	X
Pain/opioid medication log	X	X	X	X	X	X	X	X
Randomization		X						
Study drug administration			X					
Pain-VAS	X		X	X*	X*	X	X	X
Incentive spirometry (done at bedside)			X	X	X			
MEQ**			X	X	X	X	X	X
Complications			X	X	X	X	X	X

*On POD1 and later, pain assessment will be done as is standard of care by hospital staff until discharge.

** Calculation of MEQ using <http://clinicalcalc.com/Opioids/>

References:

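### Unblinded coordinators, who hold the allocation list, are also responsible for data collection, so post-discharge pain, home opioid use and judgement-dependent complications are open to ascertainment bias that a blinded statistician cannot remove

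*Combined protocol and SAP*

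**What the plan says.** Section 3.1 describes the trial as single-blind. Section 3.4.4(2) specifies who is blinded: "The subject(s) and study statistician(s) will remain blinded to the treatment assignments throughout the course of the study". It then names those who know the arm: "while the surgical team and coordinators will not be blinded". One list covers all 200 patients. It goes to the pharmacy and "will also be stored by the Research Coordinators for reference". The same paragraph has the patient ID, the assignment and the screening weight sent to the pharmacy. The protection against bias that it offers is: "Data will be analyzed by the blinded statistician(s) to ensure minimal bias".

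Section 6 then states: "Study coordinators will be responsible for data collection and will ensure that forms are completed and signed". The forms include the adverse event and medication logs.

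Table 1 schedules the VAS, the "Pain/opioid medication log", the morphine-equivalent calculation and complications at Day 30, 6 months and 12 months. Section 7 says that follow-up adverse events are obtained "either in person or through review of subjects' EHRs and phone interviews", with review by the principal investigator and co-investigators. No section provides a blinded outcome assessor or a blinded adjudicator of complications.

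**The concern.** Read together, Sections 3.4.4(2) and 6 put data collection in the hands of people who know each patient's arm. A blinded analyst protects against choices made during analysis. If one arm has been questioned more closely, or its charts searched harder, the difference is already in the database and the analyst will reproduce it faithfully.

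The exposed data are the post-discharge ones. Section 1.1 presents chronic pain, opioid use and cost as what sets this trial apart from other registered work, and Section 5 plans a between-arm test of opioid use at 6 and 12 months. A modest difference in these outcomes would be open to the criticism that it arose in how the data were gathered.

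**Working it through.** **1. Which outcomes are exposed, and how much**

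- *Follow-up VAS.* Section 2.1.2 defines it as self-reported, and the patients are blinded. Knowledge of the arm can act only through prompting, clarifying and transcribing. Limited risk.
- *Home opioid use.* Also reported by blinded patients, but it depends on recall and on how far the questioner probes. Exposed at elicitation and recording.
- *Complications and adverse events.* Several items in Section 4.3 have objective thresholds: death, return to the operating room, ventilation beyond 24 hours, air leak beyond 5 days, ICU stay beyond 24 hours. Small risk. Infection can rest on antibiotic treatment as well as on a culture, so it needs judgement. It is the clearest exposed item.
- *Morphine conversion.* Section 4.1 and Table 1 name an online calculator but not who uses it. Once drug and dose are recorded, the step is largely mechanical.
- *Inpatient pain from postoperative day 1.* The footnote to Table 1 assigns this to hospital staff, whose blinding is not stated. It lies outside this point.

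**2. Do the coordinators need the arm?** Section 3.4.4(2) gives the pharmacy its own copy of the list, and Section 3.4.3(2) has the pharmacy dispense by assignment. The ID and screening weight are enough for a request.

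**3. Reproducing the plan's power figures, to fix the method**

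Inputs from Sections 3.3 and 5: Wilcoxon rank-sum test, alpha 0.05 (taken as two-sided), 75 per arm. Power comes from the noncentral t distribution with n multiplied by the rank-sum efficiency 3/π for normal data:

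- degrees of freedom = 2n(3/π) − 2
- noncentrality = d × √(n(3/π)/2)

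For n = 75: 75 × 3/π = 71.62; √(71.62/2) = 5.984; degrees of freedom = 141.2. At d = 0.5 the noncentrality is 2.992 and the power 0.844, against the stated 0.84. The same method gives 31 per group at d = 0.862 and 49 at d = 0.6825 for power 0.90, both as stated.

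**4. Illustration of an assumed bias**

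The documents give no bias size. Let unblinded collection shift a continuous outcome by b SD between arms, with no true effect. Replacing d by b gives the probability of a significant result at 75 per arm:

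| b (assumed) | noncentrality | rejection rate |
|---|---|---|
| 0 | 0 | 5.0% |
| 0.05 | 0.299 | 6.0% |
| 0.10 | 0.598 | 9.1% |
| 0.20 | 1.197 | 22.1% |
| 0.30 | 1.795 | 43.0% |

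At 100 per arm and b = 0.20 the rate is 28.0%, so more patients make it worse. These figures apply to rank-sum outcomes such as pain scores. Section 5 compares complications, and opioid use at 6 and 12 months, by chi-squared or Fisher tests, and the table does not cover those.

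**The case against.** The design is openly declared single-blind, so there is no contradiction. That stands: this is an avoidable risk, not an inconsistency.

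The patients are blinded and rate their own pain. This also stands and limits the VAS part, but it gives no protection when complications are taken from charts.

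Being responsible for data collection could mean oversight and transcription, and the plan does not say who asks the follow-up questions. That is fair; the data collection forms are not in the text available. But the plan names nobody else for the task and nobody blinded.

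The bias size is assumed. It is, and the table shows only what would follow from a shift of that size.

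Withholding the list may not keep coordinators blind. Section 3.4.1 draws patient data from the health record, Section 3.4.4(4) puts dose deviations in the medical record, and pain-management cost is an outcome, so the chart may show the product. The investigators who review adverse events include the surgical side. This stands and makes any blind partial. It does not justify giving coordinators the whole list.

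A reader might infer that the 72-hour primary outcome is itself measured unblinded through the morphine conversion. The documents do not support this: they do not say who converts, and knowledge of the arm has little to act on in a calculator step.

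**Conclusion.** The concern holds for eliciting and recording post-discharge pain and home opioid use, and for ascertaining judgement-dependent complications and adverse events, at Day 30, 6 months and 12 months. The blinded statistician does not address it. It rests on reading Sections 3.4.4(2) and 6 together, with the coordinators as the people who collect these data.

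The size of any bias is unknown. If it were 0.1 to 0.3 SD on a continuous outcome with no true effect, the rejection rate at 75 per arm would be 9% to 43% instead of 5%; at 0.05 SD it would be 6%. No rate is claimed for the chi-squared outcomes.

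A reader might go further and conclude that no follow-up difference could be told apart from bias. That is too strong, given blinded patients and several complications with objective thresholds. The change is worth making because it is cheap and the information withheld is not needed for the coordinators' task.

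**What to change.** Amend Section 3.4.4(2), with matching text in Section 6:

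- Only the pharmacy holds the allocation list. Coordinators send it the patient ID and screening weight, and the pharmacy reads off the arm.
- Coordinators who collect outcomes are not told the arm until the 12-month data are locked.
- The study-drug page and the intraoperative drug and cost data are completed by the pharmacy or surgical team and kept apart until lock.
- Follow-up pain and opioid questions are asked from a fixed script, and the answers are recorded before the operative or medication record is opened.
- Any unblinding of a coordinator is logged.
- The report states that the blind was partial for complications and adverse events, because the chart may show the product and the reviewing investigators stay unblinded.

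Cost: a wording change, re-routed drug and cost pages, a short script and a log. Withholding the list needs no new staff, and the sample size and stated power are unchanged. Coordinators lose the ability to cross-check dispensing, which pharmacy accountability under Section 3.4.3(3) has to cover. The change reduces the risk and does not remove it.

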3.4.5. Assessment periods and associated observations and measurements

Described in schedule of assessments in Table 1

3.4.6. Concomitant Medications during the Study

(1) Prohibited Concomitant Medications Prior to Study Treatment:

Any chronic/habitual use of narcotics or within one period before consent and screening will be exclusionary. Any use of narcotics between screening and operative day, will be classified as screen failure (if not randomized) or withdrawn (if randomization has been done).

(2) Concomitant Medications during the Study

Details of all home medications, pain management medications, and anti-nausea medications will be recorded.

4. STUDY VARIABLES

4.1. Efficacy

Percentage of subjects with one or more components of a major morbidity. (up to Day 30 post operation). Components of morbidity:

- a. **MED usage** (Morphine Equivalent Dose, the amount of morphine an opioid dose is equal to using <http://clincalc.com/Opioids/>)
- b. **VAS** for Pain (Visual Analog Scale)

4.2. Safety

The following safety variables will be assessed in this study per the DSMP (Data Safety Monitoring Plain:

- a. Adverse events, serious adverse events (SAEs), and discontinuations due to AEs.
- b. Physical examination
- c. Vital signs.

4.3. Clinical

- a. **Postoperative mortality** (defined as the deaths occurring during primary hospital stay or prior to 30th postoperative day).
- b. **Additional surgical intervention** (defined as having to reenter the operating room because of bleeding, pneumothorax, prolonged air leak, or any other complication associated with primary surgery).
- c. **Prolonged mechanical ventilation** (defined as mechanical ventilation that exceeds 24 hours from closure until extubation).
- d. **Prolonged air leak** (defined by the STS Thoracic Surgery Database as an air leak that persists for greater than 5 post-operative days).

- e. **Complications** including cardiac such as cardiac tamponade, atrial fibrillation, or cardiac herniation.
- f. **Infection** (defined as presence of surgical incision infection, abscesses, pneumonia, or blood stream infections or sepsis. This could be patients who are treated with antibiotics, or show a positive culture.
- g. **Stroke** (defined as neurological deficits of abrupt onset made by clinical diagnosis that were caused by a disruption of cerebral blood flow).
- h. **Prolonged hospital stay** defined as 5 days post operatively
- i. **Prolonged ICU stay** defined as ICU stay longer than 24 hours post operatively, or reentering the ICU before 30-day post-operative follow up.

5. STATISTICAL METHODS AND DETERMINATION OF SAMPLE SIZE

Based on the results of the Parascondola et al study, a power analysis was performed to determine the necessary sample size in the 2 treatment arms for the proposed study. While the Parascondola study only examined inpatient narcotic use for the first 72 hours post-op, we plan to include all narcotic usage in this time period as the primary outcome of the proposed study. The estimated difference between the groups at 72 hours produced an effect size of $d=0.862$. This effect size would only require a sample size of 31 in each group to achieve a power of .90 to detect a statistically significant difference for $\alpha=0.05$. Given the attrition in the Parascondola study, it would seem advisable to view this effect size as having a certain degree of unreliability associated with it. Therefore, we also examined the magnitude of the difference in treatment groups which was observed at the 60 hour time point ($d=0.503$). Using the mid-point of $d=0.6825$, 49 subjects per group would be required to have statistical power=0.90 for $\alpha=0.05$. Even if the underlying effect size were $d=0.5$, a sample size of 75 per group would have power=0.84 with $\alpha=0.05$. This sample size ($n=75/\text{group}$) should also provide reasonable power to detect significant differences for the secondary outcomes of pain assessment at 24, 48 and 72 hours, as well as the cumulative pain score at 72 hours (area under the curve - AUC_{72}). Sample size determination was made using G*Power 3.1.9.2. (Faul, F., Erdfelder, E., Buchner, A., & Lang, A.-G. (2009). Statistical power analyses using G*Power 3.1: Tests for correlation and regression analyses. Behavior Research Methods, 41, 1149-1160.)

Statistical Methods

Descriptive statistics including means (standard deviations), medians (interquartile ranges – IQRs) and frequencies (counts / percentages) will be used to present the baseline characteristics for the 2 groups. Independent group's t-tests, Wilcoxon rank-

sum tests and chi-squared tests of independence (or exact tests as appropriate) will be used to compare baseline characteristics of the 2 groups to assess effectiveness of randomization. Wilcoxon rank-sum tests will also be used to test for differences between the groups on the primary outcome measure, cumulative narcotic use over the first 72 hours post-op, as well as secondary outcomes including pain scores, length of stay and cost. Chi-squared tests, or Fisher's exact tests will be used to compare the proportions of patients in the 2 groups experiencing complications or using opioids at 6 and 12 months.

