2.1. Efficacy Outcomes Measured

2.1.1. *Primary Outcomes*

- i. Total morphine equivalents consumed during 72 hours post-op

2.1.2. *Secondary Outcomes*

- i. Patient self-reported pain visual analog scale score
- ii. Narcotic or pain medications consumed throughout hospitalization and during first 30 days, 6 months and 1 year post-lobectomy
- iii. Incidence of Paresthesia
- iv. Time until first opioid usage
- v. Anti-emetic usage
- vi. Length of hospital stay
- vii. Postoperative complications (e.g. pneumonia, pulmonary complications, wound infections etc.)
- viii. Time to ambulation
- ix. Time to first bowel movement
- x. Time to chest tube removal
- xi. Peak expiratory flow measurements
- xii. Intraoperative versus postoperative pain management costs
- xiii. Overall Hospital Cost

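### Pain and cost are compared only by unadjusted rank-sum tests, so the screening Pain-VAS is left out of the outcome analysis and no cost difference in currency is planned

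*Combined protocol and SAP*

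**What the plan says.** Section 5, Statistical Methods, gives one method for the continuous outcomes: "Wilcoxon rank-sum tests will also be used to test for differences between the groups on the primary outcome measure", and the same test is extended to "secondary outcomes including pain scores, length of stay and cost". It names no covariate, no estimate of the difference between arms and no confidence interval. Means and medians are planned for baseline characteristics only. The one stated use of baseline data is to "compare baseline characteristics of the 2 groups to assess effectiveness of randomization".

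The sample-size text in Section 5 refers to "secondary outcomes of pain assessment at 24, 48 and 72 hours" "as well as the cumulative pain score at 72 hours". Table 1 marks Pain-VAS at Baseline/Screening as well as on the day of surgery, on each postoperative day, at discharge, and at day 30, 6 months and 12 months. A pre-treatment pain score therefore exists for every subject who follows the schedule.

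Section 2.1.2 lists two cost outcomes: "Overall Hospital Cost", and a comparison of the costs of pain control during and after surgery. Section 1.1 makes hospital cost an aim of the study and links the comparison of charges to the finances of the hospital and its patients.

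**The concern.** There are two separate losses.

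**Pain.** A pre-randomization measure of the outcome is often its best predictor. Using it as a covariate can increase power without recruiting anyone. The plan collects the score but gives it no role in comparing the arms. If adjustment is decided only after the data are seen, the choice of covariate is open to challenge.

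**Cost.** A rank-sum p-value does not say how much money is saved or lost per patient, whatever the shape of the cost distribution. If the arms differ in spread, it can also point away from the difference in means. A prolonged-acting drug could plausibly change the number of long, expensive stays without moving the typical one. Choosing between a mean and a median difference after seeing the data would invite selective reporting.

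**Working it through.** **1. The plan's own figures.** Inputs from Section 5: d=0.862, 0.6825 and 0.5; 31, 49 and 75 per group; alpha 0.05, taken as two-sided. For a Wilcoxon test under a normal parent, replace n by n×3/π and use noncentral-t power with noncentrality d×sqrt(n×3/π/2).

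| n per group | d | n×3/π | Noncentrality | Power | Plan states |
|---|---|---|---|---|---|
| 31 | 0.862 | 29.60 | 3.316 | 0.903 | 0.90 |
| 49 | 0.6825 | 46.79 | 3.301 | 0.904 | 0.90 |
| 75 | 0.5 | 71.62 | 2.992 | 0.844 | 0.84 |

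A plain t-test would need 30 and 47 per group and give 0.860. The sample size was thus computed for the test that is planned.

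**2. Pain.** Assumptions: d=0.5 (which Section 5 uses for narcotic consumption, not pain), 75 per arm, and a screening-to-outcome correlation ρ that the documents do not give. Adjustment multiplies residual variance by 1−ρ², so d becomes 0.5/sqrt(1−ρ²): 0.510, 0.524 and 0.577 at ρ=0.2, 0.3 and 0.5. With the formula in step 1, power is 0.858, 0.876 and 0.929. Simulation of rank ANCOVA (ranks of the outcome on arm and ranks of the screening score; 10,000 trials) agrees:

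| ρ | Rank-sum | Rank ANCOVA | Rank-sum, about 60% zeros at screening | Rank ANCOVA, about 60% zeros |
|---|---|---|---|---|
| 0 | 0.839 | 0.836 | 0.827 | 0.825 |
| 0.2 | 0.837 | 0.852 | 0.839 | 0.849 |
| 0.3 | 0.845 | 0.877 | 0.837 | 0.860 |
| 0.5 | 0.849 | 0.924 | 0.842 | 0.899 |

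Type I error of rank ANCOVA was 0.045 to 0.052. Ranks do not change under a monotone transformation, so right-skewing the same scores leaves both rank methods as they are; that is so by construction and is not evidence of robustness. ANCOVA on raw scores is a poorer choice if scores are skewed: at log-SD 0.7 its power was 0.761, 0.782 and 0.800 at ρ=0, 0.2 and 0.3.

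**3. Cost.** The documents give no cost mean or SD. Assumption: lognormal costs, 75 per arm, 20,000 simulations. With equal means, the ratio of medians is exp((0.5²−s²)/2), which is 0.946 at s=0.6 and 0.823 at s=0.8. The rank-sum test responds to that shift.

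| Scenario | Log-SDs | Rank-sum rejects | Welch rejects |
|---|---|---|---|
| Equal means | 0.5, 0.5 | 5.0% | 5.1% |
| Equal means | 0.5, 0.6 | 9.3% | 5.1% |
| Equal means | 0.5, 0.8 (extreme) | 40.8% | 5.5% |
| Equal medians, means differ by 21.5% | 0.5, 0.8 (extreme) | 5.4% | 27.6% |
| Mean 30% higher | 0.8, 0.8 | about 51% | about 41% |

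The last row matters: with equal spread and a true difference, both tests address the same shift and the rank-sum has more power.

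**4. Width of the cost interval.** With a common log-SD s, the half-width as a share of mean cost is 1.976×sqrt(exp(s²)−1)×sqrt(2/75).
- s=0.5: 1.976×0.533×0.1633 = 17.2%
- s=0.6: 1.976×0.658×0.1633 = 21.2%
- s=0.8: 1.976×0.947×0.1633 = 30.6%

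**The case against.** The strongest reply is that nothing here is wrong. The rank-sum test is valid, the sample size was built for it, and these are secondary outcomes. That stands. A reader might infer bias, an invalid test or an underpowered trial; step 1 of the working rules that out.

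The gain for pain may also be small. Section 3.3.1 excludes chronic and recent extensive narcotic users, so screening pain may sit near zero. In that case the gain is 1.0 point at ρ=0.2 (0.849 against 0.839) and 2.3 points at ρ=0.3 (0.860 against 0.837). In hospital, more than 75 per arm may be available, because Section 3.3 randomizes 200 and counts losses up to one year; at 100 per arm the unadjusted test already has power 0.930 at d=0.5. These points limit the size of the benefit, but the cost is one degree of freedom.

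On cost, a reader might conclude that the rank-sum test misleads and should be replaced. The documents do not support that: they give no cost distribution, the 41% figure needs a spread contrast that is extreme, and with equal spread the rank-sum is the more powerful test. Nor do they name the arithmetic mean as the target. That is an inference from the interest in hospital finances in Section 1.1.

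A reader might also take the Table 1 footnote, "On POD1 and later, pain assessment will be done as is standard of care by hospital staff until discharge", to mean that a different pain instrument is used in hospital. The row is labelled Pain-VAS and Section 2.1.2 names a visual analog scale, so the footnote is at most ambiguous. Rank adjustment does not need a common scale in any case.

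**Conclusion.** The point holds as a cheap improvement to the secondary analyses. It shows no error and does not reach the primary analysis, where the Wilcoxon test matches the sample size.

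The cost part is the firmer one. As written, the plan yields no between-arm cost figure in currency although cost is a stated aim, and this is true without any distributional assumption. How far the rank-sum and the mean comparison could diverge depends on assumed lognormal costs and unequal spread.

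The pain part is a possible gain of unknown size: from nil at zero correlation to about 7 or 8 points at ρ=0.5 (0.924 against 0.849, or against the design value of 0.844), given d=0.5 and 75 per arm. The documents supply neither the correlation nor an effect size for pain.

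**What to change.** Amend Section 5 before the arms are compared.

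1. **Pain at 24, 48 and 72 hours, AUC72, day 30, 6 months and 12 months.** Prespecify a rank-based ANCOVA: ranks of the outcome on arm and ranks of the Baseline/Screening Pain-VAS. Use the screening score and not the day-of-surgery score, whose timing relative to the end-of-surgery injection Table 1 does not state. Keep the unadjusted rank-sum as sensitivity analysis. Report the Hodges-Lehmann difference with 95% CI in scale units, labelled as the unadjusted companion estimate, and note that it may not agree exactly with the adjusted p-value.
2. **Cost.** Keep the rank-sum test. Beside it, report the difference in arithmetic mean cost with a bootstrap 95% CI for each cost outcome, and state that the mean is the quantity of interest.

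The change needs plan wording and a little programming, with no new data or patients. Its downsides are one degree of freedom, a cost interval that may be wide (step 4), and a percentile bootstrap that is slightly liberal: 5.1% to 6.6% rejection with equal means in the lognormal simulations (3,000 trials of 1,000 resamples).
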